6.12.9. Tanner Stage Scale

The Tanner Stage Scales are a series of line drawings that are designed to aid the investigator in appropriately assessing the sexual maturity of the subject. Data gathered will be assessed to determine that no pubertal disruption has occurred during the study. Although the line drawings were originally intended for child self-assessment, evidence suggests that pubertal assessment by the child or the parents/legal guardian is not a reliable measure of exact pubertal staging, and should be augmented by a physical examination (Rasmussen et al. 2015). The drawings will be used by the dermatologist investigator as an aid.

For each of the staging assessments (breasts in females, genitals in males, and groin/pubic for both, the Tanner Stage Score ranges from 1 to 5.

Shift table will be produced showing the number and percentage of patients shifting from the stage score at baseline to the highest postbaseline stage score by gender for each scale item for the Safety Population, OLE Period Population, and the LTE Safety Population.

A by-patient listing of Tanner stage data will be provided.

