Tanner Stage Scale		X					X	Assessment only for participants 8 years or older. Once the participant reaches the score of 5 on this scale, no further assessments are needed.
EQ-5D-Y		X			X		X	Assessment only for participants 4 years or older.
Children's Depression Inventory 2 Short Form (CDI-2)		X		X	X		X	Assessment only for participants 7 years of age or older
Pain Numeric Rating Scale		X	X	X	X	X	X	
Morning Joint Stiffness Duration		X	X	X	X	X	X	
Parent's Global Assessment of Well-Being		X	X	X	X	X	X	
Laboratory Tests								
Acute phase reactant (hsCRP)		X	X	X	X	X	X	
Acute phase reactant (ESR)		X	X	X	X	X	X	To be performed locally and before the study drug administration at Week 16
RF	X							RF test not required if past result available.
HLA-B27				X				HLA-B27 test not required if past result is available.

QuantiFERON®-TB Gold, T-Spot or PPD (if applicable)	X							See Section 9.4.5 for details.
	Screening	Open-Label Treatment Period					Notes	
Visit No	V1	V2 Baseline	V3	V4	V5	V6	V7	Baseline laboratory samples should be taken before administration of investigational product.
Study Week		W0	W2	W4	W8	W12	W16	
Study Days (Approximately)	-42 to -7d	0	14 ± 7d	28 ± 7d	56 ± 7d	84 ± 7d	112 ± 7d	
Read PPD (if applicable)	X							See Section 9.4.5 for details. To be performed locally.
Chest x-ray	X							Only for participants with a positive or repeated not negative TB test(s) and according to local guidelines. See Section 9.4.5 for details
HIV/HCV	X							HCV antibody positive results require a follow-up test for HCV RNA. See Section 5.1.1 for details.
HBV (HBsAg, HBcAb, HBsAb)	X					X		Positive test for HBcAb requires a follow-up test for HBV DNA. See Section 5.1.1 for details.
Serum pregnancy test	X							Section 5.1.1 for details. Performed centrally. Females only.
Urine pregnancy test		X		X	X	X	X	Section 5.1.1 for details. Performed locally. Females only.
Clinical chemistry	X	X		X			X	
Hematology	X	X		X			X	
Urinalysis	X	X		X			X	May not be feasible in younger (non-toilet trained) participants. Failure to obtain will not be considered a protocol violation.
Cell flow cytometry panel (B, T, CD4+T, CD8+T, and NK cells)		X					X	Participants may not have flow cytometry testing due to blood volume limitations.
Immunogenicity testing		X		X		X	X	See Section 9.6.1. All samples for immunogenicity should be taken pre-dose when applicable and possible.

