9.4.2. Tanner Stage Scale

The Tanner Stage Scales are a series of line drawings that are designed to aid the participant or caregiver in appropriately assessing the sexual maturity of the participant at the time of the visit (Chavarro et al. 2017). Participants 8 years and older will be assessing their sexual maturity according to the Schedule of Activities (Section 2).

Once the participant reaches the score 5 in the scale, no further assessments are needed.

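### The Tanner shift table takes no account of age, so it cannot support the SAP's stated aim of determining that no pubertal disruption occurred, and the SAP and protocol disagree on who does the rating

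*SAP*

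**What the plan says.** SAP 6.12.9 states the aim as "Data gathered will be assessed to determine that no pubertal disruption has occurred during the study". It then plans two outputs.

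- A shift table counting "patients shifting from the stage score at baseline to the highest postbaseline stage score by gender for each scale item", for the Safety, OLE Period and LTE Safety Populations. For each item, "the Tanner Stage Score ranges from 1 to 5".
- A listing: "A by-patient listing of Tanner stage data will be provided".

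The only other Tanner summary is the baseline distribution of stages in SAP Table RHCG.6.2, which is also not broken down by age. Pubertal disruption is not defined, and no reference for stage at a given age is named. SAP 6.12.6, by contrast, converts weight, height and BMI to z-scores and percentiles by age and sex.

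The open-label treatment schedule says of the scale: "Assessment only for participants 8 years or older. Once the participant reaches the score of 5 on this scale, no further assessments are needed".

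On the rater, the SAP says that "pubertal assessment by the child or the parents/legal guardian is not a reliable measure of exact pubertal staging", that such ratings should be supplemented by a physical examination, and that a dermatologist investigator will use the drawings as an aid. Protocol 9.4.2 says: "Participants 8 years and older will be assessing their sexual maturity".

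**The concern.** Whether puberty is disturbed is a question about stage relative to age, and about progress over time. The planned table shows stage change within a period, but nothing in it says whether a child is late or early for age. The SAP nevertheless words the purpose as a conclusion of no harm. Growth and development are a secondary endpoint of the long-term extension, and treatment can run to Week 264, so a statement about puberty is likely to be read as part of the pediatric safety evidence. If it rests on this table alone, it is not supported.

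The rater matters for the same reason. The SAP describes an investigator-assisted rating and calls child or parent staging unreliable, while the protocol collects the kind of rating the SAP warns about.

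**Working it through.** The Tanner section states no sample size, error rate or expected frequency, so there is no figure to reproduce. The check is on what the table can distinguish.

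**Inputs.** Cell definition: SAP 6.12.9. Assessment from age 8: protocol schedule of activities. Enrolment up to under 18 years: Protocol 6.1. Period lengths of 16, 88 and 160 weeks: protocol synopsis.

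**Step 1: what fixes a cell.** A participant's cell is set by period, sex, scale item, baseline stage and highest post-baseline stage. Age is absent.

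**Step 2: hypothetical trajectories, each pair within one period (girls, breast item).**

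| Trajectory | Stages | Cell |
|---|---|---|
| Age 8, prepubertal | 1, 1, 1 | 1 to 1 |
| Age 15, never enters puberty | 1, 1, 1 | 1 to 1 |
| Age 11, no change over a short interval | 2, 2, 2 | 2 to 2 |
| Age 15, halted at stage 2 | 2, 2, 2 | 2 to 2 |
| Age 12, normal progression | 2, 3, 3 | 2 to 3 |
| Age 12, later lower rating | 2, 3, 2 | 2 to 3 |

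In the first two pairs, age alone separates the children, and the table does not carry it. In the third, taking the highest stage hides the later drop.

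**Step 3: how full the no-change cells would be with normal children.** The documents give no duration for a stage, so assume a mean of m years, with m from 0.5 to 2, and exponentially distributed durations. The share of normally progressing children with no change over T years is exp(−T/m).

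- OLT: T = 16/52.18 = 0.31 years; exp(−0.31/0.5) = 0.54 to exp(−0.31/2) = 0.86.
- OLE: T = 88/52.18 = 1.69 years; 0.03 to 0.43.
- LTE: T = 160/52.18 = 3.07 years; 0.00 to 0.22.

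The overlap is large in the OLT, ranges from small to substantial in the OLE, and is smaller in the LTE. This covers children already moving through stages; those still at stage 1 because they are young add to the 1 to 1 cell.

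**Step 4: baseline.** SAP 6.1.2.2.1 resets the OLE safety baseline to about Week 16. SAP 6.1.2.3 defines the LTE baseline as a window from Visit 1 to the first LTE injection, and 6.12.9 does not say which Tanner value in that window is used. No stated table follows progression from Week 0 through Week 104.

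**Step 5: rater.** Protocol 9.4.2 describes the drawings as an aid for the participant or caregiver, and the schedule lists the scale among patient- and parent-administered measures. The planned physical examination excludes pelvic and breast examination (Protocol 9.4.1), so it does not provide the supplement the SAP calls for. Protocol Appendix 3 describes the investigators as physicians experienced in rheumatology and pediatric rheumatology, which does not match a dermatologist.

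**The case against.** The strongest reply is that the SAP ties its aim to the data gathered, not to the shift table. A by-patient listing is planned in the same section and a demographics listing in SAP 6.6.1. With about 100 participants, a reader could join age to stage by hand and, if stages are listed by visit, see any later lower rating. This stands as far as it goes. But neither the Tanner listing's fields nor any rule for reviewing it is stated, so it does not say what would count as disruption.

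Other safeguards exist: height, weight and BMI are standardised by age and sex, and the data monitoring committee reviews growth. They do not address pubertal stage directly. It is also true that finer tables will be sparse, and that setting unreliable ratings against age adds only modest certainty. That favours age bands and a descriptive aim.

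Several stronger readings are tempting, and the documents do not support them.

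- *The plan could never reveal disruption.* This fails because the listing exists, and because an LTE table lying wholly on the diagonal would look abnormal under the Step 3 assumptions.
- *A child followed for 16 weeks shares a cell with one followed for two years.* The populations belong to separate periods, so follow-up length is partly separated.
- *Participants already at stage 5 swell the no-change cells.* The schedule requires no further assessment once stage 5 is reached, so most would have no later value.
- *Arrest after onset looks like prepuberty.* It falls in the 2 to 2, 3 to 3 or 4 to 4 cells, alongside normal short-interval non-progressors.
- *Using the highest stage always conceals a reversal.* In the OLT the scale is taken only at Weeks 0 and 16, so highest equals last.

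**Conclusion.** The concern holds in a limited form. The one post-baseline summary in SAP 6.12.9 cannot separate failure to enter or progress through puberty from non-progression that is normal for age, and so cannot carry the stated conclusion. That follows from the table's definition and needs no assumption. The percentages in Step 3 are illustrative and rest on the assumed stage durations. The listing could help but, as specified, supplies no criterion. The mismatch over who rates is a direct contradiction between the SAP and the protocol. The primary endpoint is unaffected; what is at risk is the strength of one safety statement. The change should be made.

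**What to change.** In SAP 6.12.9:

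- Present the shift table by age band; for the OLE and LTE, give it also from the Week 0 baseline.
- Show last as well as highest post-baseline stage, and state the denominator as those below stage 5 at baseline.
- Add age at each assessment to the by-patient listing, calculated from the collected date of birth. The 1 July imputation in the footnote to SAP Table RHCG.6.2 can be off by about half a year.
- Replace the aim of determining that no disruption occurred with *describe pubertal progression relative to age*.
- Reconcile the rater description with Protocol 9.4.2.

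The cost is SAP wording and one extra table from data already collected (date of birth, sex, stage), with no new procedure. The cells will be sparse in about 100 participants, and the conclusion will be more modest.

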6.12.10. Uveitis

At each study visit, the investigator will ask the patient/caregiver whether they developed uveitis since the last visit and evaluate the patient for any symptoms of acute anterior uveitis since the last visit as specified in the protocol Schedule of Activities. If the patient has no prior

ophthalmologist-diagnosed uveitis and develops eye pain or discomfort, eye redness, blurring of vision, or any other symptoms suggestive of acute anterior uveitis, the patient must be evaluated by an ophthalmologist. It is expected that all children with JIA will be on screening and regular evaluation with ophthalmologists based on local/regional/national guidelines.

Uveitis data will be captured using uveitis CRF. Percent of patients reporting uveitis will be summarized at each scheduled visit for patients with or without prior uveitis, separately. The analysis periods and populations are specified in [Table RHCG.6.12](#). No imputation will be used. A by-patient listing of uveitis data will be provided as well.

6.12.11. Special Safety Topics

Safety information on special topics including AESI will be presented by treatment group and by study period. [Table RHCG.6.16](#) provides the definitions/derivations and analyses methods (including analyses, summaries and by-patient listings) of special safety topics including AESIs.

Potential AESIs will be identified by a standardized MedDRA query (SMQ) or a Lilly-defined MedDRA PT listing. Preferred terms within an SMQ will be classified as broad and narrow. In the Lilly-defined MedDRA PT listings, Lilly has provided the broad and narrow classification. The Lilly-defined broad terms are for a more sensitive search of potential events of interest and the Lilly-defined narrow terms are for a more specific search. Therefore, the summaries will include the classifications of broad term (same as pooling narrow and broad terms together) and narrow term. In the event that the listing of terms or analysis changes for a special safety topic, it will be documented in the program safety analysis plan (PSAP) which will supersede this document; it will not warrant an amendment to the individual study SAP.

Table RHCG.6.16. Definitions and Analyses of Special Safety Topics

Special Safety Topic	Definition / Derivation	Analysis / Summary / Listing
Hepatic	
Hepatic AE analysis will include events that are potentially drug-related hepatic disorders by using the MedDRA PTs contained in any of the following SMQs:
 
 • Broad and narrow terms in the Liver related investigations, signs and symptoms (20000008) • Broad and narrow terms in the Cholestasis and jaundice of hepatic origin (20000009) • Broad and narrow terms in the Hepatitis, non-infectious (20000010) • Broad and narrow terms in the Hepatic failure, fibrosis and cirrhosis and other liver damage (20000013) • Narrow terms in the Liver-related coagulation and bleeding disturbances (20000015) 
The number and percentages of patients with the following elevations in hepatic laboratory tests at any time will be summarized between treatment groups:
 
 • The number and percentages of patients with an ALT or AST measurement ≥ 3 times (3\times), 5 times (5\times), 10 times (10\times), and 20 times (20\times) the Performing lab ULN during the treatment period will be summarized for all patients with a post-baseline value. 
 ◦ The analysis of 3 \times ULN will contain four subsets: patients whose non-missing maximum baseline value is $\leq 1 \times$ ULN, patients whose maximum baseline is $>1 \times$ ULN but $<3 \times$ ULN, patients whose maximum baseline value is $\geq 3 \times$ ULN, and patients whose baseline values are missing. ◦ The analysis of 5 \times ULN will contain five subsets: patients whose non-missing maximum baseline value is \leq to 1 \times ULN, patients whose maximum baseline is $>1 \times$ ULN but $<3 \times$ ULN, patients whose maximum baseline is $\geq 3 \times$ ULN but $<5 \times$ ULN, patients whose maximum baseline value is $\geq 5 \times$ ULN, and patients whose baseline values are missing. ◦ The analysis of 10 \times ULN will contain six subsets: patients whose non-missing maximum baseline value is $\leq 1 \times$ ULN, patients whose maximum baseline is $>1 \times$ ULN but $<3 \times$ ULN, patients whose maximum baseline is $\geq 3 \times$ ULN but $<5 \times$ ULN, patients whose maximum baseline is $\geq 5 \times$ ULN but $<10 \times$ ULN, patients whose maximum baseline value is $\geq 10 \times$ ULN, and patients whose baseline values are missing. 	
OLT Period (Safety Population): TEAE by PT within SMQ or sub-SMQ
 
OLE Period (OLE Period Population): TEAE by PT within SMQ or sub-SMQ
 
LTE Period (LTE Safety Population): TEAE by PT within SMQ or sub-SMQ
 
Listing (Safety Population): TEAE
 
Listing (Safety Population): Elevations in hepatic laboratory tests


Special Safety Topic	Definition / Derivation	Analysis / Summary / Listing
	
 ○ The analysis of $20 \times \text{ULN}$ will contain seven subsets: patients whose non-missing maximum baseline value is $\leq 1 \times \text{ULN}$, patients whose maximum baseline is $>1 \times \text{ULN}$ but $<3 \times \text{ULN}$, patients whose maximum baseline is $\geq 3 \times \text{ULN}$ but $<5 \times \text{ULN}$, patients whose maximum baseline is $\geq 5 \times \text{ULN}$ but $<10 \times \text{ULN}$, patients whose maximum baseline is $\geq 10 \times \text{ULN}$ but $<20 \times \text{ULN}$, patients whose maximum baseline value is $\geq 20 \times \text{ULN}$, and patients whose baseline values are missing. ● The number and percentages of patients with a total bilirubin measurement $\geq 1.5 \times$, and $\geq 2 \times$ the Performing lab ULN during the treatment period will be summarized for all patients with a post-baseline value. 
 ○ The analysis of $1.5 \times \text{ULN}$ will contain four subsets: patients whose non-missing maximum baseline value is $\leq 1 \times \text{ULN}$, patients whose maximum baseline is $>1 \times \text{ULN}$ but $<1.5 \times \text{ULN}$, patients whose maximum baseline value is $\geq 1.5 \times \text{ULN}$, and patients whose baseline values are missing. ○ The analysis of $2 \times \text{ULN}$ will contain five subsets: patients whose non-missing maximum baseline value is $\leq 1 \times \text{ULN}$, patients whose maximum baseline is $>1 \times \text{ULN}$ but $<1.5 \times \text{ULN}$, patients whose maximum baseline is $\geq 1.5 \times \text{ULN}$ but $<2 \times \text{ULN}$, patients whose maximum baseline value is $\geq 2 \times \text{ULN}$, and patients whose baseline values are missing. ● The number and percentages of patients with an ALP measurement $>1.5 \times$ the Performing lab ULN during the treatment period will be summarized for all patients with a post-baseline value, and divided into four subsets: patients whose non-missing maximum baseline value is $\leq 1 \times \text{ULN}$, patients whose maximum baseline is $>1 \times \text{ULN}$ but $\leq 1.5 \times \text{ULN}$, patients whose maximum baseline value is $>1.5 \times \text{ULN}$, and patients whose baseline values are missing. ● The number and percentages of patients meeting the following elevated hepatic criteria: maximum ALT $\geq 3 \times \text{ULN}$ and maximum Total Bilirubin $\geq 2 \times \text{ULN}$ during the treatment period will be summarized. 
Shift tables (or scatterplots) will be produced showing the number and percentage of patients with a maximum post-baseline result in each of the categories below, by treatment group and baseline result. Note that for these tables, a single maximum baseline time point will be used. Maximum baseline will be the maximum non-missing observation in the baseline period. The maximum post-baseline value will be the maximum non-missing value from within each
	
Listing (Safety Population): Shift in hepatic laboratory tests


Special Safety Topic	Definition / Derivation	Analysis / Summary / Listing
	
treatment period. Scheduled visits, unscheduled visits, and repeat measurements will be included. Such shift tables will be produced for the following parameters and categories:
 
 • ALT; $\leq 1 \times \text{ULN}$, >1 to $<3 \times \text{ULN}$, ≥ 3 to $<5 \times \text{ULN}$, ≥ 5 to $<10 \times \text{ULN}$, ≥ 10 to $<20 \times \text{ULN}$, and $\geq 20 \times \text{ULN}$. • AST; $\leq 1 \times \text{ULN}$, >1 to $<3 \times \text{ULN}$, ≥ 3 to $<5 \times \text{ULN}$, ≥ 5 to $<10 \times \text{ULN}$, ≥ 10 to $<20 \times \text{ULN}$ and $\geq 20 \times \text{ULN}$. • Total bilirubin; $\leq 1 \times \text{ULN}$, >1 to $<1.5 \times \text{ULN}$, ≥ 1.5 to $<2.0 \times \text{ULN}$, $\geq 2.0 \times \text{ULN}$. • ALP; $\leq 1 \times \text{ULN}$, >1 to $\leq 1.5 \times \text{ULN}$, $>1.5 \times \text{ULN}$. 
In addition, the number and percentage of patients with maximum post-baseline results will be presented overall and by treatment group for each treatment period within the following classes:
 
 • Decreased; post-baseline category $<$ baseline category. • Increased; post-baseline category $>$ baseline category. • Same; post-baseline category $=$ baseline category. 	
	
Elevated hepatic criteria: maximum ALT $\geq 3 \times \text{ULN}$, maximum total bilirubin $\geq 2 \times \text{ULN}$.
 
Listing of patients who meet any of the following criteria:
 
 • Elevated hepatic criteria: defined as maximum ALT $\geq 3 \times \text{ULN}$, maximum total bilirubin $\geq 2 \times \text{ULN}$ • An ALT or AST $\geq 3 \times \text{ULN}$ • An ALP $\geq 1.5 \times \text{ULN}$ • A total bilirubin $\geq 2 \times \text{ULN}$ 
The listing will include: patient demographics, concomitant medications, ALT/AST/ALP/total bilirubin/GGT by visit, treatment start and stop dates, and reason for treatment discontinuation
	
Listing (Safety Population): Elevations in hepatic criteria

	
Evaluation of Drug-Induced Serious Hepatotoxicity (eDISH) plot: To further evaluate potential hepatotoxicity, an eDISH plot will be created. Each patient with at least 1 post-baseline ALT and total bilirubin contributes 1 point to the plot. The maximum ALT measurement and the maximum total bilirubin measurement after the first injection will be included. Patients will be classified into 2 groups: never on ixekizumab or ever on ixekizumab. The measurements do not need to be taken at the same blood draw. There will only be 1 eDISH plot for each indication, regardless of treatment periods.
	
Figure (Safety Population): eDISH plot (display in Spotfire)
 
Figure (OLE Period Population): eDISH plot (display in Spotfire)
 
Figure (LTE Safety Population): eDISH plot (display in Spotfire)

Cytopenias	
Cytopenias will be defined using the PTs from the following 2 sub SMQs of the Haematopoietic cytopenias SMQ (20000027) as defined in MedDRA Version:
 
 • Broad and narrow terms in the Haematopoietic leukopenia (20000030) 	
OLT Period (Safety Population): TEAE by PT within sub-SMQ

Special Safety Topic	Definition / Derivation	Analysis / Summary / Listing
	
 Broad and narrow terms in the Haematopoietic thrombocytopenia (20000031) 
The number and percentage of patients with TEAEs will be summarized by treatment group using MedDRA PT nested within SMQ. Two summaries will be created: (1) pooling narrow and broad terms together, and (2) narrow terms only. Events will be ordered by decreasing frequency in ixekizumab group (or combined ixekizumab group in the event of multiple cohorts/doses) nested within SMQ.
	
OLE Period (OLE Period Population): TEAE by PT within sub-SMQ
 
LTE Period (LTE Safety Population): TEAE by PT within SMQ or sub-SMQ
 
Listing (Safety Population): TEAE

Infections	
Infections are events including all infections (defined using all the MedDRA PTs from the Infections and infestations SOC), serious infections, potential opportunistic infections, and infections resulting in anti-infective medication administration (i.e., antibacterial, antiviral, antifungals, antiparasitic treatment.) as defined in Appendix 5.
 
The relationship between TEAEs-infections and other clinical, laboratory, and hematology parameters will be examined using Spotfire tool.
	
OLT Period (Safety Population): TEAE by PT SAE by PT DCAE by PT
 
OLE Period (OLE Period Population): TEAE by PT SAE by PT DCAE by PT
 
LTE Period (LTE Safety Population): TEAE by PT SAE by PT DCAE by PT
 
Listing (Safety Population): TEAE

	
The opportunistic infections (OI) are defined in Appendix 6. This list contain PTs as contained within Categories (narrow or broad) from the infections and infestations SOC and from the investigations SOC which can assist in identifying potential OIs. The narrow terms are considered opportunistic infections unless medical review determines that the reported term is not consistent with the patient's clinical history/presentation/course. Medical review of broad terms is needed for final determination of patients meeting the program definition of OIs. The number and percentage of patients with TEAEs that represent potential OIs will be summarized by treatment group using MedDRA PT nested within categories. Events will be ordered by decreasing frequency in the ixekizumab group (or combined ixekizumab group in the event of
	
OLT Period (Safety Population): TEAE of OIs by PT
 
OLE Period (OLE Period Population): TEAE of OIs by PT
 
LTE Period (LTE Safety Population): TEAE of OIs by PT

Special Safety Topic	Definition / Derivation	Analysis / Summary / Listing
	
multiple cohorts/doses) nested within categories. The relationship between TEAEs-infections and other clinical, laboratory, and hematology parameters will be examined using Spotfire tool.
 
The duration of each common TEAE PT of Infections and narrow terms for Opportunistic infections will be evaluated by treatment group using Spotfire. Duration is defined as follows:
 $\text{Duration of treatment-emergent AE-Infections (in weeks)} = (\text{End date of AE} - \text{Start date of AE} + 1) / 7.$ 
Patients who do not have the PT will not be included in the analysis. If the TEAE has not ended by the date of completion from the study, or date of early discontinuation, it will be censored as of that date. If a patient has multiple episodes of the same TEAE, the episode with the greatest severity will be used for the duration of event calculation. If a patient has multiple episodes of the same TEAE with the same severity, the episode with the longest duration will be used for the duration of event calculation.
	
Listing (Safety Population): TEAE of OIs
 
OLT Period (Safety Population): Duration of Common TEAE – Infections (additional display in Spotfire)
 
OLE Period (OLE Period Population): Duration of Common TEAE – Infections (additional display in Spotfire)
 
LTE Period (LTE Safety Population): Duration of Common TEAE – Infections (additional display in Spotfire)

Allergic Reactions/Hypersensitivities	
Allergic reactions/hypersensitivity events will be categorized as either anaphylaxis or non-anaphylaxis events (these will refer to events that are not localized to the site of injection) and summarized separately. Medical reviews are needed for final determination of patients with allergic reactions/hypersensitivities.
 
Allergic/Hypersensitivity Events, Anaphylaxis. Anaphylaxis has been broadly defined as “a serious allergic reaction that is rapid in onset and may cause death” (Sampson et al. 2006). Identification of cases of potential anaphylaxis from the clinical trial data involves two screening criteria, one designed to specifically identify cases (following Criterion 1) based on narrow terms from the MedDRA SMQ for anaphylactic reaction (20000021), and the second to identify possible cases, following Criterion 2 as defined by Sampson et al. (2006).
 
Criterion 1 for anaphylaxis is defined by the presence of a TEAE based on the following MedDRA PTs from the anaphylactic reaction SMQ:
 
 • Anaphylactic reaction • Anaphylactic shock • Anaphylactoid reaction • Anaphylactoid shock • Kounis Syndrome 	
OLT Period (Safety Population): TEAE by PT within Category SAE by PT within Category AE leading to discontinuation of study drug within Category
 
OLE Period (OLE Period Population): TEAE by PT within Category, SAE by PT within Category AE leading to discontinuation of study drug within Category
 
LTE Period (LTE Safety Population): TEAE by PT within Category SAE by PT within Category AE leading to discontinuation of study drug within Category

Special Safety Topic	Definition / Derivation	Analysis / Summary / Listing
	
 • Type 1 hypersensitivity 
Criterion 2 for anaphylaxis requires having TEAEs from 2 or more of 4 categories of AEs as described by Sampson et al. (2006). Occurrence of these events should be nearly coincident; based on recording of events on eCRFs. All qualifying events must be within 1 day of study drug injection. The 4 categories to be considered in Criterion 2 are:
 
 • Category A: Involvement of the skin-mucosal tissue • Category B: Respiratory compromise • Category C: Reduced blood pressure or associated symptoms • Category D: Persistent gastrointestinal symptoms 
The specific MedDRA PTs covered by each of these Criterion 2 categories are shown in Appendix 7. Summaries of Criterion 2 anaphylactic TEAEs will be provided by the specific combination of categories as follows:
 
 • AB: events based on meeting Category A and Category B (but no other category); • AC: events based on meeting Category A and Category C (but no other category); • AD: events based on meeting Category A and Category D (but no other category); • BC: events based on meeting Category B and Category C (but no other category); • BD: events based on meeting Category B and Category D (but no other category); • CD: events based on meeting Category C and Category D (but no other category); • ABC: events based on meeting Category A, Category B and Category C (but no other category); • ABD: events based on meeting Category A, Category B and Category D (but no other category); • ACD: events based on meeting Category A, Category C and Category D (but no other category); • BCD: events based on meeting Category B, Category C and Category D (but no other category); • ABCD: events based on meeting each of the 4 Criterion 2 categories. 
Summaries of treatment-emergent anaphylactic AEs will be provided for patients meeting each of the 2 criteria and for patients who meet either criteria overall. Separate summaries will be provided for TEAEs by maximum severity, SAEs, and AEs resulting in study drug discontinuation. Severity of treatment-emergent Criterion 2 anaphylactic AEs will be based on the maximum severity of the specific events met by the patient. Maximum severity of an (overall) treatment-emergent anaphylactic AE will be based on the maximum severity within Criterion 1 and/or Criterion 2.
	
Listing (Safety Population): TEAE

Special Safety Topic	Definition / Derivation	Analysis / Summary / Listing
	
Allergic Reactions/Hypersensitivity Events, Non-Anaphylaxis: TEAEs of allergic reaction/hypersensitivity categorized as non-anaphylaxis events are defined by the narrow terms within Hypersensitivity SMQ (20000214) excluding the PTs noted in Appendix 8 and excluding the anaphylactic events as defined above.
	
Injection Site Reactions	
Injection site reactions will be defined using the PTs from the MedDRA High Level Term Injection Site Reactions as defined by MedDRA excluding the following 10 PTs (the excluded PTs were determined by the most current MedDRA Version):
 
 1) Embolia cutis medicamentosa 2) Injection site joint discomfort 3) Injection site joint effusion 4) Injection site joint redness 5) Injection site joint infection 6) Injection site joint inflammation 7) Injection site joint movement impairment 8) Injection site joint pain 9) Injection site joint swelling 10) Injection site joint warmth 
The Injection Site Reaction eCRF page captures the injection site reactions identified by the investigator.
 
Redness (Scored 0-4)
 
 [0] Subject's normal skin color, no increased redness [1] Noticeable, but very mild redness [2] Clearly red [3] Bright red [4] Dark with some scar formation 
Swelling (Scored 0-4 after running a finger over injected area)
 
 [0] No bump [1] Barely noticeable [2] Clear bump but very thin [3] Clear bump 1 mm thick 	
OLT Period (Safety Population): TEAE by PT within HLT, SAE by PT within HLT (additional display in Spotfire), AE leading to treatment discontinuation by PT within HLT (additional display in Spotfire)
 
OLE Period (OLE Period Population): TEAE by PT within HLT, SAE by PT within HLT (additional display in Spotfire), AE leading to treatment discontinuation by PT within HLT (additional display in Spotfire)
 
LTE Period (LTE Safety Population): TEAE by PT within HLT, SAE by PT within HLT (additional display in Spotfire), AE leading to treatment discontinuation by PT within HLT (additional display in Spotfire)
 
Listing (Safety Population): TEAE (additional display in Spotfire)

Special Safety Topic	Definition / Derivation	Analysis / Summary / Listing
	
[4] Clear bump 2 mm thick or more
 
Pain (including burning) (Scored 0-3)
 
 [0] None [1] Mild [2] Moderate [3] Severe 	
OLT Period (Safety Population): TEAE by maximum severity TEAE by maximum redness category TEAE by maximum swelling category TEAE by maximum pain category
 
OLE Period (OLE Period Population): TEAE by maximum severity TEAE by maximum redness category TEAE by maximum swelling category TEAE by maximum pain category
 
LTE Period (LTE Safety Population): TEAE by maximum severity TEAE by maximum redness category TEAE by maximum swelling category TEAE by maximum pain category

Malignancies	
Malignancies will be defined using PTs from the Malignant or unspecified tumors SMQ as defined in MedDRA (SMQ: 20000091, which includes the sub-SMQs:
 
 • 20000194 [Malignant tumours], including sub-SMQs of 20000227 [Haematological malignant tumours] and 20000228 [Non-haematological malignant tumours] • 20000195 [Tumours of unspecified malignancy], including sub-SMQs of 20000229 [Haematological tumours of unspecified malignancy] and 20000230 [Non-haematological tumours of unspecified malignancy] 
The number and percentage of patients with TEAEs will be summarized by treatment group using MedDRA PT nested within the following categories:
 
 • Non-Melanoma Skin Cancer (NMSC) 
 ◦ Basal Cell Carcinoma, 
 ▪ PTs include: Basal cell carcinoma, Basosquamous carcinoma, and Basosquamous carcinoma of skin 	
OLT Period (Safety Population): TEAE by PT within Category
 
OLE Period (OLE Period Population): TEAE by PT within Category
 
LTE Period (LTE Safety Population): TEAE by maximum severity TEAE by maximum redness category TEAE by maximum swelling category TEAE by maximum pain category

Special Safety Topic	Definition / Derivation	Analysis / Summary / Listing
	
 ○ Squamous Cell Carcinoma: 
 ▪ PT: Squamous cell carcinoma of skin, Bowen's disease, Lip squamous cell carcinoma, Skin squamous cell carcinoma metastatic, and Keratoacanthoma ● Malignancies excluding NMSC: all PTs in the Malignant or unspecified tumors SMQ excluding the 8 defined NMSC PTs. 	Listing (Safety Population): TEAE
Depression and Suicide/self-injury	
Depression and suicide/self-injury will be defined using the PTs from the Depression and Suicide/self-injury SMQ as defined in MedDRA (SMQ: 20000035, which includes the sub-SMQs: 20000037 [Suicide/self-injury] and 20000167 [Depression (excl suicide and self-injury)]).
	OLT Period (Safety Population): TEAE by PT within SMQ and sub-SMQ OLE Period (OLE Period Population): TEAE by PT within SMQ and sub-SMQ LTE Period (LTE Safety Population): TEAE by PT within SMQ or sub-SMQ Listing (Safety Population): TEAE
Inflammatory Bowel Disease	
Inflammatory Bowel Disease (IBD) will be externally adjudicated by the Central Events Committee (CEC). The CEC will adjudicate investigator-reported events selected for adjudication and render an assessment as to whether the event represents a confirmed event (meeting the event definition with all necessary documentation). If an adjudicated result is "definitive" or "probable" event then the event is considered positively adjudicated. All events positively adjudicated will be used for the analysis of IBD. The categories and subcategories of reported events used for the adjudication will can be found below.
 
Inflammatory Bowel Disease (IBD) will be identified using the following subcategory and MedDRA PTs: The narrow terms are considered IBD. Medical reviews of broad terms are needed for final determination of patients with IBD.
 
IBD (Narrow terms)
 
 ● Inflammatory Bowel Disease: Inflammatory bowel disease ● Crohn's Disease: Crohn's disease ● Ulcerative Colitis: Acute haemorrhagic ulcerative colitis; Colitis ulcerative; Proctitis ulcerative 
Non-Specific Terms: The PTs in this category are listed in Appendix 9.
	OLT Period (Safety Population): IBD (included in AE overview) OLE Period (OLE Period Population): IBD confirmed by adjudication (included in AE overview) LTE Period (LTE Safety Population): IBD (included in AE overview) Listing (Safety Population): TEAE

Special Safety Topic	Definition / Derivation	Analysis / Summary / Listing
Interstitial Lung Disease	
Interstitial Lung Disease will be defined using the PTs:
 
 • Narrow terms in the Interstitial lung disease SMQ (20000042); • The following 6 PTs from the Eosinophilic Pneumonia SMQ (20000157) will also be included in the analyses: 
 1) Angiolympoid hyperplasia with eosinophilia (Narrow), 2) Eosinophilic bronchitis (Narrow), 3) Hypereosinophilic syndrome (Narrow), 4) Loeffler's syndrome (Narrow), 5) Pulmonary eosinophilia (Narrow), 6) Pulmonary vasculitis (Narrow). 	
OLT Period (Safety Population): TEAE by PT within Category
 
OLE Period (OLE Period Population): TEAE by PT within Category
 
LTE Period (LTE Safety Population): TEAE by PT within Category
 
Listing (Safety Population): TEAE

Abbreviations: AE = adverse event; ALP = alkaline phosphatase; ALT = alanine aminotransferase; AST = aspartate aminotransferase; DCAE = discontinuation due to adverse event; eCRF = electronic case report form; HLT = high-level term; LTE = long-term extension; MedDRA = Medical Dictionary for Regulatory Activities; OLE = open-label extension; OLT = open-label treatment; PT = preferred term; SAE = serious adverse event; SMQ = standardized MedDRA query; SOC = System Organ Class; TEAE = treatment-emergent adverse event; ULN = upper limit of normal.

